10.2 Sample Size, Accrual Time and Study Duration

Power and Sample Size Considerations. Sample size for this study was estimated using a 2-group test of non-inferiority of proportions, with the 2-year invasive breast cancer rate in the surgery group assumed to be 0.10 based on published studies.^{61,62} The non-inferiority margin assumed was 0.05. Based on a 1-sided un-pooled z-test, with alpha=0.05, a sample size of n=446 per group will have 80% power⁶⁴ to detect the specified non-inferiority margin. The proportion of patients who decline the arm to which they are specifically randomized can diminish the estimate of treatment difference, and could also widen the confidence bounds, but the analytical approaches proposed here aim to diminish the impact on bias of the treatment difference. With a 3-year duration of accrual and 2 additional years of follow-up, we anticipate approximately 148 total events.

Analysis of Primary Outcome (See below for outcomes definitions). This trial was designed anticipating non-acceptance of arm allocation, and the proportion of patients that do not accept their arm allocation can lead to bias in estimates of treatment differences. Thus, we plan to complete several analyses of the primary outcome, reporting the primary intent to treat (ITT) analysis as well as sensitivity analyses that are intended to reduce the bias in estimation of treatment difference in this setting.

We assume that a clinically acceptable difference in 2-year invasive cancer diagnosis rate in order to conclude non-inferiority is 5%. Cumulative incidence curves will be used to estimate the invasive cancer diagnosis rates over time, and at the 2-year point, the difference in rates will be estimated and a 1-sided upper confidence bound of (AM-GCC) will be computed, using methods described by Austin.⁶⁵ We will conclude that AM is not inferior to Surgery if the upper confidence bound on the risk difference at 2 years is less than 5%.

ITT Analysis. The ITT analysis of 2-year invasive cancer diagnosis rate will be conducted using all patients, as randomized, and will be completed using Kaplan-Meier estimates, stratified by group, combined with the Greenwood's confidence interval. The difference in invasive cancer risks will be computed from the Cox model with treatment at 2 years, with a 1-sided 95% confidence interval of the difference (AM-GCC) computed.

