- (iii) *distant breast cancer metastasis if none* of the following events have occurred previously: ipsilateral invasive breast cancer, contralateral invasive breast cancer, ipsilateral lymph node cancer, contralateral lymph node cancer.
- (iv) *breast cancer death if none* of the following events have occurred previously: ipsilateral invasive breast cancer, contralateral invasive breast cancer, ipsilateral lymph node cancer, contralateral lymph node cancer, distant breast cancer metastasis.

Ipsilateral breast event (in situ or invasive) is defined as first occurrence of either of the following:

- (i) *ipsilateral invasive breast cancer* (see definition above)
- (ii) *ipsilateral in situ breast cancer*

Censoring vs Ignoring of events

For all time to event analysis (Kaplan-Meier, Cox models), we have to assign to each occurrence one of the following actions (Table 3):

Time to event outcome	Ipsilateral invasive breast event	Ipsilateral breast event	Disease-specific survival	Overall survival
Ipsilateral invasive in-breast cancer	Event	Event	Ignore	Ignore
Ipsilateral in situ in-breast cancer	Ignore	Event	Ignore	Ignore
Contralateral invasive in-breast cancer	Ignore	Ignore	Ignore	Ignore
Contralateral in situ in-breast event cancer	Ignore	Ignore	Ignore	Ignore
Ipsilateral lymph node cancer	Event if no prior iINV	Event if no prior iINV	Ignore	Ignore
Contralateral lymph node cancer	Ignore	Ignore	Ignore	Ignore
Distant breast cancer metastasis	Event if no prior iINV or cINV or cLX or iLX	Event if no prior iINV or cINV or cLX or iLX	Ignore	Ignore
Death from breast cancer	Event if no prior iINV or cINV or cLX or iLX or DistMet	Event if no prior iINV or cINV or cLX or iLX or DistMet	Event	Event
Death from breast-cancer unrelated cause	Censor	Censor	Censor	Event
Loss to follow-up	Censor	Censor	Censor	Censor

Table 3. See SLBE coding section for abbreviations of iINV, cINV, iLX, cLX and DistMet

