Planned subgroup analyses (NCDB Special Study). The large DCIS registry developed through collaboration with the National Cancer Database (NCDB) will allow for the continued collection of long-term outcomes for patients as well as for the comparison of primary and secondary outcomes (when measurable in NCDB) for **AM versus surgery** amongst those patients who are randomized and accept their arm allocation versus those patients who are randomized but do not accept their arm allocation versus patients not registered or randomized to COMET, but who generally meet our broad inclusion criteria for the trial. Patients will be identified from all study sites during the time interval of COMET accrual. These analyses will be from predominantly non-randomized patients, so we plan to utilize observational study approaches for analyses. We will use full regression models (logistic or Cox model, dependent upon outcome measure) to control for potential confounders, including pathology, age, race, academic versus community setting, among others. As in other analyses, we will utilize inverse-probability weighting to handle missing data.⁷⁰

Analyses of long-term outcomes. Analyses of long-term outcomes will follow the approaches outlined above, modifying the year of rate calculations, accordingly. PRO data will utilize longitudinal linear mixed models over time, following appropriate scoring and transformation, if needed.

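### Long-term ipsilateral cancer rates: Kaplan-Meier with unrelated deaths censored overstates the proportion diagnosed, modestly and mainly in the AM arm at 10 years

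*Combined protocol and SAP*

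**What the plan says.** Four places in the protocol bear on this point.

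- Section 10.2, Analysis of Primary Outcome: "Cumulative incidence curves will be used to estimate the invasive cancer diagnosis rates over time".
- Section 10.2, ITT Analysis: the 2-year analysis "will be completed using Kaplan-Meier estimates, stratified by group", with Greenwood's interval. The arm difference and its one-sided bound come from a Cox model.
- Section 10.2, Table 3, which covers all time-to-event analyses: the row "Death from breast-cancer unrelated cause" is set to censor for the ipsilateral invasive event, the ipsilateral event and disease-specific survival. It is an event for overall survival only.
- Section 10.2, long-term outcomes: "Analyses of long-term outcomes will follow the approaches outlined above, modifying the year of rate calculations, accordingly". Section 2.3.2 lists ipsilateral invasive cancer rates at 5, 7 and 10 years.

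No competing-risk method is mentioned anywhere. The planned sensitivity analyses deal with refusal of allocation, withdrawal and loss to follow-up.

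**The concern.** Section 2.3.1 defines the primary endpoint as a proportion of women diagnosed, and the later rates are the same quantity at longer horizons. A woman who dies of another cause can no longer be diagnosed. Censoring her treats her as if she remained at the same risk as the women still followed. One minus Kaplan-Meier therefore estimates risk in a setting without other deaths, and it exceeds the real proportion whenever such deaths come before possible diagnoses. A Cox-derived risk difference that uses the same censoring inherits the problem.

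The gap grows with time. Entry is from age 40 with no upper limit, one stratum is over 65, and follow-up runs to 10 years. The gap can also differ between arms. Upstaging in the surgery arm is found at operation, expected within 60 days of randomization, before many competing deaths can occur. Diagnoses under AM can accrue over years. What is at stake is the accuracy of the long-term absolute rates and of their difference.

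**Working it through.** **1. The plan's own figure.** Section 10.2 gives: "Based on a 1-sided un-pooled z-test, with alpha=0.05"; "with the 2-year invasive breast cancer rate in the surgery group assumed to be 0.10"; "The non-inferiority margin assumed was 0.05"; and "a sample size of n=446 per group will have 80% power". With equal true rates,

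n = (1.6449 + 0.8416)² × 2 × 0.10 × 0.90 / 0.05² = 445.1, rounded up to 446 per group.

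This reproduces. A constant hazard of −ln(0.9)/2 = 0.0527 per year, uniform 3-year accrual plus 2 years and 892 women give 149 events, against about 148 stated. Neither calculation includes competing deaths.

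**2. Assumptions.** The documents give no other-cause mortality for this trial and no event rates after 2 years. I assume:

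- other-cause mortality D of 5-20% by 10 years, with constant hazard m = −ln(1 − D)/10;
- AM arm: 10% by 2 years (λ₁ = 0.0527), then λ₂ = 0.02 per year;
- surgery arm: 10% found at day 60, plus a background of 0.005 per year.

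The only guide in the documents is the cited DCIS trial of tamoxifen and radiotherapy in section 1.2.2: 11% deaths overall and 2% from breast cancer, so 11 − 2 = 9% other deaths, with no follow-up time given.

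**3. One minus Kaplan-Meier at 10 years.**

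- AM: 1 − 0.9 × exp(−8 × 0.02) = 23.3%
- Surgery: 1 − 0.9 × exp(−10 × 0.005) = 14.4%

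**4. Cumulative incidence at 10 years.** For AM,

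C = λ₁/(λ₁+m) × [1 − exp(−2(λ₁+m))] + exp(−2(λ₁+m)) × λ₂/(λ₂+m) × [1 − exp(−8(λ₂+m))].

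With D = 10%, m = 0.01054 and C = 0.0990 + 0.1251 = 22.4%, an excess of 0.90 points. For surgery, the parts before, at and after day 60 are 0.0008 + 0.0997 + 0.0409 = 14.2%, an excess of 0.24 points.

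| Other-cause death by 10 years | AM cumulative incidence | AM excess | Surgery cumulative incidence | Surgery excess | Inflation of AM − surgery |
|---|---|---|---|---|---|
| 5% | 22.9% | 0.45 | 14.3% | 0.12 | 0.33 |
| 9% (cited trial, if over 10 years) | 22.5% | 0.81 | 14.2% | 0.21 | 0.59 |
| 10% | 22.4% | 0.90 | 14.2% | 0.24 | 0.66 |
| 20% | 21.5% | 1.84 | 13.9% | 0.49 | 1.35 |

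Excesses are percentage points from unrounded values.

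**5. Earlier horizons, same 5-20% range.**

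| Year | AM excess | Surgery excess |
|---|---|---|
| 2 | 0.05-0.22 | 0.01-0.06 |
| 5 | 0.14-0.61 | 0.04-0.16 |
| 7 | 0.24-1.02 | 0.06-0.27 |

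The 2-year difference moves by 0.04-0.16 points, against a margin of 5 points.

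**The case against.** The best case for the plan has five parts.

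- **The Kaplan-Meier sentence is about 2 years.** There the effect is negligible. The extension rests on one general sentence, and the approaches it refers back to also include cumulative incidence curves. That is fair, and the term may loosely mean one minus Kaplan-Meier, in which case the wording does not conflict. But Table 3 governs every time-to-event analysis and censors unrelated death, so the overstatement follows on either reading unless a competing-risk estimator is named.
- **The effect is small.** With 540 women per arm (1,080/2), the standard error of a 20% rate is √(0.2 × 0.8/540) = 1.7 points before censoring. Good performance status and fitness for surgery are required, so 20% mortality looks high. This stands, and it is why the point is minor. It does not make a systematic, avoidable bias acceptable.
- **The direction is conservative.** In these illustrations the error counts against AM, so it would not help AM to be declared non-inferior. This stands for the comparison. It does not help the accuracy of the absolute rates.
- **A reader might infer an excess of 1-2 points in both arms.** A constant hazard reaching 20% by 10 years, with 10-20% other-cause mortality, does give cumulative incidences of 19.0-18.0%. That assumes events spread over the decade. The documents place the surgery arm's 10% at operation, which few deaths can precede.
- **A reader might infer that contralateral cancer and mastectomy rates are certainly overstated.** Table 3 has no column for either, so their censoring rule is not stated and can only be inferred from the long-term sentence.

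**Conclusion.** The point holds as a minor one about the 5-, 7- and 10-year ipsilateral rates. The direction is mathematical: with unrelated deaths censored, one minus Kaplan-Meier cannot fall below the proportion diagnosed and exceeds it once such deaths precede later events. The size depends on assumed mortality and post-2-year hazards. With 5-20% other-cause death by 10 years, it is about 0.4-1.8 points for AM, 0.1-0.5 for surgery and 0.3-1.4 in the difference.

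The documents do not support reading this as a threat to the primary result or the sample size. Nor do they support a claim about rates in older women specifically: age is a stratification factor but not a listed subgroup, and nothing says that AM is most relevant to that group. Overall survival is unaffected, because all deaths are events there.

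**What to change.** 1. In Table 3, change death from a cause unrelated to breast cancer from censored to a competing event for both ipsilateral outcomes.
2. State that the 5-, 7- and 10-year absolute rates, their arm difference and its confidence bound come from the Aalen-Johansen cumulative incidence. Using it at 2 years as well keeps the method consistent, with negligible numerical effect.
3. Keep cause-specific Cox models for hazard ratios and Kaplan-Meier for overall survival.
4. Add columns to Table 3 for contralateral invasive cancer and mastectomy, with the same competing-event coding.

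No new data are needed, since section 10.8 already records date and cause of death. The cost is slightly more analysis work and a documented change of the stated estimator, including the source of the arm difference, which now comes from a Cox model.

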6.1.2 Imaging Assessment Plan

Clinical criteria for DCIS progression and indications for biopsy or treatment will be left to the best clinical judgment of the treating provider, together with the patient. ***Pragmatic clinical criteria requiring additional work up include the following:***

- New breast mass on clinical examination in either breast
- Other new breast signs including nipple/skin retraction, nipple discharge, breast edema/erythema in either breast.

Radiographic criteria for DCIS progression and indications for biopsy or treatment will be left to the best clinical judgment of the treating provider, together with the patient and breast imagers at each site.

Pragmatic radiographic criteria for biopsy recommendation during follow up are the following:

- New **mass/architectural distortion*/density*** on mammogram in either breast according to *ACR Breast Imaging Reporting and Data System (BI-RADS) for mammography in assessment of masses and calcifications.⁶³
- Increase in extent of calcifications $\geq 5\text{mm}$ in at least one dimension compared to the most recent prior MMG in the index breast.
- New **suspicious** findings on other radiologic studies (US, MRI) in either breast (i.e. hypoechoic area).

For all routine mammograms, patients will be informed of the result of the mammogram within 1 week of the date of the mammogram. If a patient fails to schedule or keep a mammogram appointment, a second appointment will be scheduled. If the patient fails to keep the second appointment, the patient will be contacted by telephone. The site research team must make every effort to ensure that patient contact details are up to date.

Diagnostic or surgical procedures other than those required by the protocol, as well as any change in management (e.g. participant in AM arm wishes to proceed with surgery in the absence of clinical and/or radiographic progression or participant in surgery arm decides not to proceed with surgery) and reason for change will be recorded, along with the findings prompting the recommendation or decision. In addition, any recommendations for management declined by the patient will also be recorded.

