7. STUDY ASSESSMENT TABLE

Laboratory and clinical parameters during treatment are to be followed using individual institutional guidelines and the best clinical judgment of the responsible physician. **There are no mandatory lab tests required for this study;** if no labs are drawn per physician discretion (based on routine site practice), that is acceptable. It is expected that patients on this study will cared for by physicians experienced in the treatment and supportive care of patients on this trial. Date of registration is Day 1 on study.

TABLE 1. Schedule of Eligibility Screening and Clinical Follow up

	Eligibility Screening	REGISTRATION	Day 1-28	Further event (DCIS or IBC) ⁸	Day 1-180	Every 6M (years 0-5)	Every 12M (years 1-5)	Every 12M (years 6-10) ⁹
Tests & Observations								
History/physical	X					X		X
Weight, height	X							
Pulse, Blood Pressure	X							
Randomization			X					
Biospecimen collection				X				
Blood sample			X	X			X ¹	X ¹
Tissue sample			X	X				
Imaging studies²								
Contralateral MMG							X (both arms)	
Ipsilateral MMG ³	X			X		X (AM arm)	X (surgery arm)	
Bilateral MMG ⁴	X							X (both arms)
Therapeutic procedures					X			
Surgery ⁵					X			
Radiation (optional) ⁶					X			
Discuss endocrine therapy (both arms)					X			
#Adverse Events⁷								
Report AEs (both arms)					X	X	X	

¹ For patients registered after August 14, 2020

² if routine bilateral MMG performed on an annual basis, it can be used for the contralateral MMG findings also (not required if patient has had mastectomy of the indicated breast)

³ ipsilateral mammogram ≤ 120 days of registration (can also include ultrasound or breast MRI)

⁴ bilateral mammogram ≤ 6 months of registration

⁵ for surgery arm only

⁶ for surgery arm only (optional)

⁷ Record any new AE (or increase of a documented pre-existing condition from screening/history) within 30 days (see also section 9.1.1 - Routine Adverse Event Reporting)

⁸ up to four weeks after a further event (DCIS or invasive breast cancer) occurs

⁹ if patient cannot attend in person, status update can be collected over the phone (patient does not have to provide blood draw or submit MMG)

All follow up visits (including imaging) will take place at scheduled month +/- 4 weeks. Time points should be based on day 1 (date of registration); however, if there is an out of window visit, all subsequent visits should use that timepoint as the date of reference.

Table 2: Schedule of PRO surveys

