Sensitivity analyses. Several sensitivity analyses are planned, including a per protocol analysis, as treated analysis, an instrumental variable analysis, as well as a principal stratification analysis.^{68,69} The sensitivity analysis will account for loss of follow-up, rejection of randomization allocation and withdrawals, and pre-randomization factors influencing rejection of randomization, described in further detail below.

Intent-to-treat (ITT) analysis is typically the standard in reporting results of clinical trials. However, in the presence of rejection of randomization allocation (here defined as selecting surgery when randomized to AM, and choosing AM when randomized to surgery), ITT results can be biased;⁶⁶⁻⁶⁸ similarly per protocol (PP) and as-treated (AT) analyses could yield biased estimates, especially since these analyses may no longer maintain balance achieved by randomization. Cuzick et al⁶⁶ outline an approach to measure treatment effect among compliers, which follows the randomization (e.g. ITT), but assures that the estimates are not diluted by allocation changes. Thus, studies using this approach are similarly powered to ITT analysis, but provide appropriately wider confidence limits, which will be critical in a non-inferiority study. Principal stratification approaches can improve upon the width of confidence intervals and can

allow for covariate adjustment to aid in this improvement. Additionally, the covariates can aid in identifying subgroups with differential clinical response or treatment preference.

We recognize the potential to lose patients to follow-up; yet, we consider approaches that could still provide some level of information for all patients who were randomized. Dunn et al⁶⁷ describe instrumental variable methods with inverse probability weighting for missing data and latent class models as two approaches to deal with loss to follow-up. Each approach makes assumptions, most of which are feasible for this trial, but we will report the assumptions as well as the comparative analyses in the literature and disseminate findings. We will also assess sensitivity to departures from these assumptions through simulation studies.

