10.7 Survival Follow up

Any study participant can choose to withdraw from the study at any time for any reason, including no specified reason. Patients in the surgery arm cannot opt for the AM arm after surgery, but in the event that a patient withdraws from the study, the date of withdrawal and reason for withdrawal will be recorded. The patient will be censored in time-to-event analyses at the date of withdrawal from the study

Patients in the AM arm may choose to either withdraw from the study or opt to proceed with surgery at any time. In the event that a patient in the AM arm opts to proceed with surgery in the absence of invasive progression, the date of withdrawal and reason for withdrawal will be recorded. As for the surgery arm, in the event that a patient withdraws from the study, the patient will be censored at the date of withdrawal from the study.

Patients in the AM arm with progression to invasive breast cancer are required by the study protocol to proceed with surgery for their invasive breast cancer. Patients who have invasive breast progression and do not wish to have surgery will continue to remain in follow up with their invasive cancer event recorded, at the time of invasive breast progression for the primary analysis. For further exploratory analyses, the lack of surgery for these patients will be recorded.

For patients who choose to no longer be followed per the protocol schedule, the patient can choose to enter the Survival Follow-up Phase. Survival data, ongoing adjuvant therapies and subsequent disease progression data will be collected during this phase of the study every 12 months for 10 years from registration. Telephone contact is acceptable as well as medical record review.

Follow-up will be discontinued early due to:

- Patient Death
- Patient Withdrawal of consent for all follow-up
- Patient deemed lost to follow-up

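### No planned analysis accounts for lapsed index-breast imaging: unimaged women on active monitoring stay at risk as event-free, which on balance favours non-inferiority

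*Combined protocol and SAP*

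**What the plan says.** **Compliance.** Section 10.2 (Sensitivity analyses) defines rejection of the allocation as follows: "here defined as selecting surgery when randomized to AM, and choosing AM when randomized to surgery". No other form of non-compliance is defined. The sensitivity analyses (per-protocol, as-treated, instrumental-variable, principal stratification) are said to address loss to follow-up, rejected allocation and withdrawal. The checks during enrolment cover withdrawal, rejected allocation and later treatment changes. The per-protocol population is not defined anywhere.

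**Censoring.** For the ipsilateral invasive endpoint, Table 3 in Section 10.2 censors for death from an unrelated cause and for loss to follow-up. Section 10.7 adds withdrawal. Section 10.8 requires at least 24 months without clinical data before a woman counts as lost, and then censors her 24 months after last contact.

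**Missed imaging.** Section 6.1.2 provides for a second appointment, and then: "If the patient fails to keep the second appointment, the patient will be contacted by telephone". It also has declined recommendations recorded. Under Section 10.7 a woman who no longer wants the visit schedule may choose annual survival follow-up, for which "Telephone contact is acceptable as well as medical record review". No analysis rule refers to completed imaging.

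**How cancers are found.** Section 2.1 puts upstaging at the operation at 10% in the surgery arm, and Section 5.1.2.1 expects surgery within 60 days. In AM, Section 6.1.1 relies on index-breast mammography and clinical examination, each every 6 months.

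**The concern.** The endpoint is a diagnosis, so a cancer in an unexcised breast counts only if it is found. Most surgery-arm cancers should be found in the excision specimen soon after randomization. Most AM cancers need an image, an examination or a symptom, followed by a biopsy. If imaging lapses while the woman stays in contact, she adds two event-free years to the AM denominator, although her status has not been observed. Weaker delivery of AM then makes AM look safer.

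The analyses meant to guard against dilution do not catch this. A complier estimate based on crossover counts her as having received AM. The planned inverse probability and latent-class methods address loss to follow-up, and she is not lost. The mode-of-monitoring subgroup compares 6-monthly mammography with additional imaging, not with absent imaging. A non-inferiority finding could then not be told apart from under-detection in AM.

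**Working it through.** **1. The plan's own design.** Section 10.2 gives these inputs: "Based on a 1-sided un-pooled z-test, with alpha=0.05"; "with the 2-year invasive breast cancer rate in the surgery group assumed to be 0.10"; "The non-inferiority margin assumed was 0.05"; "a sample size of n=446 per group will have 80% power". With equal true rates of 10%:

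n = (1.645 + 0.842)² × (0.10×0.90 + 0.10×0.90) / 0.05² ≈ 446 per arm, with power 80.1%.

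The stated sample size is reproduced. The enrolment figure of 1,080 gives 1,080/2 = 540 per arm, so both sizes are used below.

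**2. Which rule applies to a woman in contact but unimaged?**

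| Rule | Applies to her? |
|---|---|
| Rejected allocation (10.2) | No, she has not had surgery |
| Unrelated death (Table 3) | No |
| Withdrawal (10.7) | No |
| Loss to follow-up (10.8) | No, clinical data are still arriving |

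She stays at risk as event-free. Even a woman with no contact after registration would be censored only at 24 months, so she too counts as event-free across the 2-year window.

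**3. Effect on the error rate.** Assumptions: the true AM rate is exactly at the margin (15%) and the surgery rate is 10%. A share f of AM women have no follow-up imaging, and a share s of their cancers is still found clinically. The documents give neither f nor s.

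- Observed AM rate: p = 0.15 × [1 − f(1 − s)]
- SE = √{[0.10×0.90 + p(1 − p)] / n}
- P(non-inferiority declared) = Φ{[0.05 − (p − 0.10)] / SE − 1.645}

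Example with n = 446, f = 10%, s = 0: p = 0.135; SE = √(0.206775/446) = 0.02153; 0.015/0.02153 − 1.645 = −0.948; Φ = 17.2%.

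| AM women unimaged (f) | Observed AM rate, s = 0.5 to s = 0 | False non-inferiority, 446 per arm | 540 per arm |
|---|---|---|---|
| 0% | 15.0% | 5.0% | 5.0% |
| 5% | 14.6% to 14.25% | 7.0% to 9.7% | 7.3% to 10.3% |
| 10% | 14.25% to 13.5% | 9.7% to 17.2% | 10.3% to 19.0% |
| 20% | 13.5% to 12.0% | 17.2% to 41.6% | 19.0% to 47.3% |

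**4. Later lapse, and the remedy.** A simulation (20,000 runs, 446 per arm, mammograms at 6, 12, 18 and 24 months, s = 0) gives smaller effects when women stop after the 6-month mammogram: 13.1% at f = 10% and 27.8% at f = 20%. Censoring at the last mammogram brings the AM estimate back to about 15.0% and the error to 5.0-5.6%, provided that stopping is unrelated to risk.

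**5. Offset from the surgery arm.** Let a share g of surgery-arm women both decline surgery and go unimaged, with the same s. If their true rate is 10%, full cancellation needs 0.10g = 0.15f, so g = 1.5f. If it is 15%, it needs g = f. The offset is complete only if the surgery arm has at least as many unexcised and unimaged women as AM has unimaged women.

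**The case against.** Several objections stand and limit the point.

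- **The quoted definition is about rejecting the allocation, not adherence in general.** A reader might infer that the plan makes unimaged women adherent in the per-protocol analysis. The documents do not say so. That population is undefined, and the bias follows only if it borrows the crossover definition.
- **The intention-to-treat analysis uses no compliance definition.** A reader might blame the definition for any bias there. The cause is the censoring rules combined with a diagnosis-based endpoint. If the target is AM as delivered, in a trial that calls itself pragmatic, lapsed imaging is part of the strategy and the estimate is not biased for that target. It does not then show that invasive cancer is no more frequent under AM, which is how non-inferiority would be read.
- **The surgery arm is not immune.** Sections 6.1.2 and 10.2 anticipate women who decline surgery. If they also skip imaging, the comparison moves the other way.
- **Unimaged does not mean unexamined.** Women who keep their visits are examined every 6 months, and new breast signs call for work-up (Section 6.1.2). Missed mammograms do not lead automatically to survival follow-up, which is the woman's choice and still collects progression data.
- **The telephone update in Table 1, footnote 9,** applies only to years 6-10. It bears on the later time points, not on the primary endpoint.

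**Conclusion.** The gap is real and its direction is, on balance, toward non-inferiority in the intention-to-treat and crossover-based complier analyses. Its size is unknown. The illustration runs from about 10-17% (446 per arm) or 10-19% (540 per arm) false non-inferiority with 10% of AM women unimaged, to about 17-42% or 19-47% with 20% unimaged, against a nominal 5%. These ranges assume a true difference exactly at the margin, no imaging from the start in the women concerned, half to none of their cancers found clinically, and no offset from the surgery arm. They are scenarios, not forecasts. A reader might take the upper figures as the expected error of the trial; nothing in the documents supports that. The design arithmetic itself is sound. This should be fixed.

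**What to change.** Add to Section 10.2:

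1. **A pre-specified sensitivity analysis** of the 2-, 5-, 7- and 10-year ipsilateral invasive rates. In either arm, an index breast not excised since randomization contributes event-free time only up to its last completed index-breast imaging, with inverse probability weights for imaging drop-out. State how a cancer found clinically after imaging has lapsed is handled; the simulation above used no follow-up beyond the last mammogram.
2. **A per-protocol definition** with an imaging-adherence criterion that counts only mammograms due before the earliest of diagnosis, surgery, death or month 24. A fixed count, such as 3 of 4 by month 24, would remove AM women diagnosed at month 6 or 12. If 15% were found evenly over four screens, the AM rate would fall to 7.5/92.5, about 8%.
3. **A table by arm** of completed index-breast mammograms.

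The data should already be there: visit forms and imaging reports (Sections 6.1.1 and 14.1) and declined recommendations (Section 6.1.2). Section 10.2 already names inverse probability weighting. No patient's care changes. The cost is wider limits in the sensitivity analysis, a slightly smaller per-protocol set, and reliance on imaging drop-out being explained by measured covariates.
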